#### 2. Study Hypotheses/Objectives

#### 2.1 Safety Objective

This study will evaluate the safety, tolerability, and dose limiting toxicities (DLTs) of a darTreg infusion for adult, de novo, liver transplant recipients who have received a T cell depleting agent and are maintained on TAC- or EVR-based Tregsupportive IS regimen.

#### 2.2 Mechanistic Objectives

This study will evaluate the effects of the Treg-supportive IS regimens on the immunological profiles of liver transplant patients. This study will also describe for the first time the persistence of administered darTregs in humans.

Confidential Page 29 of 80

#### 3. Study Design

#### 3.1 Description of Study Design

This is a multi- center, open-label, dose- escalation, pilot study in which adult subjects undergoing primary solitary liver transplant will receive a T cell depletion agent (Thymoglobulin®) followed by Treg-supportive IS regimen based on either EVR or reduced-dose TAC (Cohorts 1a and 1b). Subjects in subsequent cohorts will also receive a single infusion of autologous, darTregs (Cohort 2: 50 million darTregs; Cohort 3: 200 million darTregs: or Cohort 4: 800 million darTregs). For individual participants, there are up to three successive stages in the study with specific eligibility criteria for each stage. As shown in *Figure* 8, the three stages are:

- Screening and Enrollment
- Eligibility assessment for EVR conversion and proceeding to T-reg infusion
- darTreg Infusion

Subjects will be followed for 40 weeks after transplant, during which clinical data along with peripheral blood (PBMCs and serum) and liver biopsy samples will be collected and analyzed (Appendix 1, 2 3).

[figure not shown]

Figure 8. Three Stages of Trial

The four cohorts are summarized below, with details about the dose escalation plan in Section 5.4.

- Cohort 1: 3 subjects from Center 1 (Cohort 1a) + 3 subjects from Center 2 (Cohort 1b); these subjects will undergo T cell depletion followed by TAC- or EVR-based IS (Stage 1 and 2; they will not receive darTreg infusion (Stage 3)).
- Cohort 2: 3 subjects meeting eligibility criteria for all 3 Stages will receive 50 million darTregs (Dose A range 25-60 million).
- Cohort 3: 3 subjects meeting eligibility criteria for all 3 Stages will receive 200 million darTregs (Dose B range 100-240 million).
- Cohort 4: 6 subjects meeting eligibility criteria for all 3 Stages will receive 800 million darTregs (Dose C range 400-960 million).

#### 3.2 Safety Outcomes

The safety, tolerability, and ties of darTreg therapy given within the context of either a TAC- or EVR-based IS regimen will be evaluated with the rate of the following events within 40 weeks of transplantation:

Clinical outcomes that will be described are:

- 1. Incidence and severity of biopsy-proven AR and/or CR (Demetris A. J., 1997) (Demetris A. D., 2000)
- 2. Incidence of ≥ Grade 3 infections as defined in Section 14.3.1
- 3. Incidence of wound complications (≥ CTCAE Grade 3)

Confidential Page 30 of 80

- 4. Incidence of anemia, neutropenia, and/or thrombocytopenia (according to study defined reporting requirements, *Section 14.3.1*)
- 5. Incidence of AEs attributable to the darTreg infusion including infusion reaction / cytokine release syndrome (CRS) (≥ CTCAE Grade 3), and malignant cellular transformation.

#### 3.3 Mechanistic Outcomes

Blood and liver biopsy samples from all patients enrolled in the study will be analyzed using MFC, T cell functional assays, and/or immunohistochemical techniques to describe the effect of TAC- vs EVR-based IS with or without darTreg administration on immune cell profiles over time. We will also describe the persistence of administered darTregs after infusion using TCR repertoire analysis as well as deuterium labeling of administered darTregs.

Mechanistic outcomes that will be assessed are:

- 1. Treg frequency in peripheral blood using Treg TruCount assay
- 2. Persistence of infused darTregs in peripheral blood and biopsies using deuterium labeling and T cell repertoire analysis
- 3. darTreg and darTconv frequency in peripheral blood using an in vitro allofrequency assay
- 4. MFC to assess effect on immune profiles
- 5. Functional assessment of Tregs in peripheral blood using a MLR suppression assay
- 6. Histology and immunophenotype of liver biopsies

Confidential Page 31 of 80

#### 4. Selection of Participants and Clinical Sites/Laboratories

#### 4.1 Rationale for Study Population

The liver transplant setting was chosen for multiple reasons. First, the liver is considered an organ of immune privilege. As such, it is the only solid organ transplant associated with an appreciable rate of spontaneous operational tolerance (Demetris A. J., 2009) (Mazariegos G., 2011). Although historical evidence was based on sporadic case reports and single center experiences (Assy, 2007) (Eason, 2001) (Girlanda, 2005) (Mazariegos G., 2011) (Mazariegos G. J., 1997) (Oike, 2002) (Orlando, 2008) (Pons, 2003) (Ramos, 1995) (Takatsuki, 2001) (Tisone, 2006) (Tryphonopoulos, 2005) (Devlin, 1998), several ongoing or recently completed clinical trials have provided strong corroborating evidence (NCT00105235; NCT00135694; NCT00320606; NCT00436722; NCT00647283; NCT00668369; NCT01198314) (Martinez-Llordella, 2008) (Bohne, 2012) ([name] S. U., 2012) (Benitez C, 2013). Emerging data from these experiences and trials indicate that the likelihood of spontaneous tolerance increases with time after transplantation with estimated frequency of <10% for patients <3 years after transplant, 10% for patients between 3–6 years after transplant, 35% for those between 6–10 years after transplant, and >80% for patients >10 years after transplant (Martinez-Llordella, 2008) (Bohne, 2012) (Benitez C, 2013). This data suggests a substantial opportunity to increase the likelihood and/or accelerate the development of tolerance through novel approaches based on rigorous biological mechanisms. Second, it is known that, among solid organ allografts, the liver is uniquely resilient to rejection processes. AR, particularly for the non-hepatitis C virus (HCV), non-autoimmune population that we aim to enroll, has not exerted a detrimental event on patient or graft survival (Wiesner, 1998). Similarly, in the modern IS era, CR not only occurs rarely (Jain, 2001) but is also amenable to treatment (Inomata, 2001) (Blakolmer K. A., 2000) (Blakolmer K. E., 1999). Third, as a corollary of the above, a basic premise underlying all of the IS withdrawal trials is that AR occurring in a highly supervised setting, such as a clinical trial, will be diagnosed and treated expeditiously, leading to rapid resolution without any long-term sequelae. Therefore, determining an optimal dose of darTregs in this pilot dose escalation trial will set the stage for a Phase II safety and efficacy trial that includes attempted IS withdrawal.

#### **MELD Score**

We have chosen MELD score of ≤25 somewhat arbitrarily as the MELD score is a continuous metric of liver disease severity. As such, there is no obvious discrete threshold. A MELD score of 25 corresponds to an approximate 20% risk of death from liver disease in 90 days. This threshold will exclude severely / critically ill patients.

Historically, the median laboratory MELD score of UCSF liver transplant recipients is 19.3 while that of Emory is significantly lower. So a threshold of 25 will exclude less than one third of all deceased donor liver transplant candidates, ensuring the feasibility of our study design.

#### **Minimum Circulating Tregs**

We are requiring a minimum threshold of circulating Tregs at the time of recruitment for a practical reason. In order to be able to manufacture a darTreg product, we will need to be able to isolate a sufficient starting population of Tregs from the liver transplant candidate through phlebotomy or leukapheresis. Patients with very low concentrations of Tregs may not yield sufficient Treg numbers to support darTreg production.

After transplantation, we do believe that we need to achieve a dominance of Tregs over Tconvs. We aim to achieve this goal by the combination of depletion and administration of increasing doses of darTregs.

#### **HLA-DR Matching**

We are excluding liver transplant recipients who are matched to their donor at both HLA-DR as this will compromise the generation of the darTreg product.

Confidential Page 32 of 80

#### 4.2 Inclusion Criteria

Subjects who meet all of the following criteria are eligible for enrollment as study participants. Inclusion criteria should be re-affirmed as appropriate at each stage of the study.

- 1. Able to understand and provide informed consent
- 2. End-stage liver disease and listed for deceased-donor primary solitary liver transplant
- 3. Between 21 and 70 years of age at the time of study entry /consent
- 4. Have a calculated MELD score ≤ 25 at the time of study entry /consent
- 5. Female and male subjects with reproductive potential must agree to use FDA approved methods of birth control for the duration of the study.
- 6. If history of HCV, have completed or are in current treatment for HCV AND have no detectable HCV RNA
- 7. Subjects with HCC meeting Milan criteria

#### 4.3 Exclusion Criteria

#### 4.3.1 Screening and Enrollment Exclusion Criteria A (Stage 1)

Below are exclusion criteria to be assessed at study enrollment, prior to **Stage 1 study procedures**. Subjects who meet any of these criteria are ineligible for study participation.

- End stage liver disease secondary to autoimmune etiology (autoimmune hepatitis, primary biliary cirrhosis, or primary sclerosing cholangitis)
- 2. History of less than 5 years remission of malignancy, except for 1) HCC or 2), history of adequately treated in-situ cervical carcinoma, or adequately treated basal or squamous cell carcinoma of the skin
- 3. History of previous organ, tissue or cell transplant
- 4. Serologic evidence of human immunodeficiency 1 or 2 infection
- 5. Epstein Barr Virus (EBV) sero-negativity (EBV naïve candidates)
- 6. Cytomegalovirus (CMV) sero-negativity (CMV naïve candidates) if donor is positive
- 7. Chronic use of systemic glucocorticoids or other IS, or biologic immunomodulators
- 8. Chronic condition requiring anti-coagulation after liver transplantation
- 9. Any chronic illness or prior treatment which, in the opinion of the investigator, precludes study participation
- 10. Participation in any other studies that involved investigational drugs or regimens in the preceding year
- 11. Received any vaccination within 28 days prior to leukapheresis or blood collection for Treg manufacture
- 12. Hemoglobin < 9.0 g/dL within 10 days prior to screening
- 13. Neutrophils <1,500/μL within 10 days prior to screening
- 14. Platelets <40,000/μL within 10 days prior to screening

#### 4.3.2 Thymoglobulin® Exclusion Criteria B (Stage 2)

Below are exclusion criteria to be assessed prior to **administration of Thymoglobulin**®. Subjects who meet any of these criteria should not receive Thymoglobulin®.

- 1. Calculated MELD score greater than 25 at the time of deceased donor liver transplant
- 2. Last AFP obtained prior to liver transplantation >400 μg/L for candidates with HCC
- 3. Unacceptable PBMC product for participants enrolled in Cohorts 2, 3, or 4, per UCSF HICTF manufacturing specifications
- 4. Absence of donor cells for manufacturing for any participant
- 5. HLA-DR matched to donor at both loci
- 6. Subject is < 21 or > 70 years of age at the time of transplantation
- 7. Located in the ICU 72 hours after transplantation
- 8. Hemoglobin < 8.0 g/dL
- Absolute neutrophil count <1,200/μL

- 10. Platelets <40,000/μL
- 11. Positive pregnancy test for females of child bearing potential
- 12. Unexpected histopathology on back table liver biopsy that contraindicates the initiation of Treg supportive IS regimen.
- 13. Development of a condition requiring chronic anti-coagulation

Confidential Page 33 of 80

- 14. Hypersensitivity to rabbit proteins or any excipient in Thymoglobulin®
- 15. Detectable HCV RNA (if history of HCV (e.g. serology positive at screen A)) or less than six months after end of treatment for HCV at the time of transplantation (i.e. does not meet criteria for SVR)

#### 4.3.3 Exclusion Criteria C1

Below are exclusion criteria to be assessed at day 30-44 after transplantation for continuation in the trial. All subjects regardless of eligibility for EVR conversion, with any of the following will not receive darTregs and will move into safety follow up.

- 1. Explanted liver with evidence of increased risk of recurrent cancer (HCC tumor burden exceeding the Milan criteria; presence of vascular invasion; cholangiocarcinoma morphology)
- 2. Insufficient depletion of recipient T cells, defined as a nadir CD3 count ≥50 cells/µL (50 cells/mcL) or total lymphocyte count ≥ 0.1 x 10^9/L if CD3 count is unavailable
- 3. Development of a condition requiring chronic anti-coagulation
- 4. Clinical evidence of untreated biliary obstruction
- 5. ALT >2.0 x upper limit of normal (ULN)
- 6. Inability to taper off corticosteroids by 44 days (+/- 2 days) after transplant
- 7. Detectable circulating HCV

#### 4.3.4 Everolimus Conversion Criteria C2 (Stage 2)

Below are exclusion criteria to be assessed prior to conversion to **EVR-based IS regimen.** Subjects who meet any of these criteria should not be converted to EVR-based IS regimen. EVR cannot be initiated prior to 30 days after liver transplantation. Subjects with any of the following will remain on TAC-based IS regimen.

- 1. Evidence of hepatic artery stenosis or thrombosis by Doppler examination or angiography within 7 days prior to conversion
- 2. Urine protein/creatinine ratio >1.0 mg/mg within 7 days prior to conversion
- 3. Calculated GFR less than 30 ml/min per MDRD4 equation within 7 days prior to conversion
- 4. Physical examination documentation of abnormal wound healing or uncontrolled wound infection
- 5. Hemoglobin <8.0 g/dL within 7 days prior to conversion
- 6. Absolute neutrophil count <1,200/μL within 7 days prior to conversion
- 7. Platelets <50,000/µL. within 7 days prior to conversion

#### 4.3.5 darTreg Infusion Exclusion Criteria D (Stage 3)

Below are exclusion criteria to be assessed prior to darTreg infusion for subjects in Cohorts 2, 3, and 4 only. Subjects in Cohort 2, 3, or 4 who meet any of these criteria should not receive a **darTreg-infusion**:

- 1. Inability or unwillingness of participant to give additional written informed consent
- 2. Unacceptable darTreg product
- 3. Detectable circulating EBV or CMV DNA within 10 days prior to darTreg infusion
- 4. Detectable HBV DNA within 10 days prior to darTreg infusion
- 5. Detectable circulating HCV RNA within 10 days prior to darTreg infusion
- 6. ALT >1.5x ULN within 10 days of darTreg infusion
- 7. Most recent, but not greater than 10 days prior to darTreg infusion, 12 hour TAC trough levels of > 8  $\mu$ g/L for all subjects
- 8. Most recent, but not greater than 10 days prior to darTreg infusion, 24 hour EVR trough levels of  $< 5 \mu g/L$  for all subjects on EVR
- 9. For subjects on EVR-based IS, received MMF within 10 days prior to darTreg infusion
- 10. Evidence of AR or CR according to Banff criteria on protocol allograft biopsy based on local assessment
- 11. Received any vaccination within 14 days prior to darTreg infusion
- 12. Positive pregnancy test for females of child bearing potential
- 13. Inability or unwillingness of participant to comply with study protocol or procedures
- 14. Calculated GFR less than 40 ml/min per MDRD4 equation within 10 days prior to infusion

Confidential Page 34 of 80

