## Exclusion Criteria (continued)

#### **Exclusion criteria D** (assessed prior to darTreg-infusion):

- 1. Inability or unwillingness of participant to give written informed consent
- 2. Unacceptable darTreg product.
- 3. Detectable circulating EBV or CMV DNA within 10 days prior to darTreg infusion
- 4. Detectable circulating HBV DNA within 10 days prior to darTreg infusion
- 5. Detectable circulating HCV RNA within 10 days prior to darTreg infusion
- 6. ALT >1.5x ULN within 10 days prior to darTreg infusion
- 7. Most recent, but not greater than 10 days prior to darTreg infusion, 12 hour TAC trough levels of  $> 8 \mu g/L$  for all subjects
- 8. Most recent, but not greater than 10 days prior to darTreg infusion, 12 hour EVR trough levels of  $< 5 \mu g/L$  for subjects on EVR
- 9. For subjects on EVR-based IS, received MMF within 10 days prior to Treg infusion
- 10. Evidence of AR or CR according to Banff criteria on allograft biopsy on local assessment
- 11. Received any vaccination within 14 days prior to darTreg infusion
- 12. Positive pregnancy test for females of child bearing potential
- 13. Inability or unwillingness to comply with study protocol or procedures
- 14. Calculated eGFR less than 40 ml/min per MDRD4 equation within 10 days prior to infusion.

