#### 5.1.3 Repeated darTregs Manufacturing

The manufacturing process can be repeated once for a particular subject if there or technical or logistical issues with the first preparation. The study team will review the available manufacturing information to determine if a second manufacturing attempt is likely to be successful. Except for liver biopsy, the laboratory components of Screen D must be repeated within 10 days of planned infusion to ensure eligibility. In any case, infusion of darTregs must take place no later than 20 weeks after transplantation. If the second attempt at manufacturing fails, the subject will go into safety follow up (Appendix 4).

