# 8.3 Liver biopsies

For all subjects, local pathology information will be obtained for assessment of eligibility criteria B (no central pathology assessment). If a pathology report is unavailable from donor records, a liver biopsy will be obtained on the back table.

For patients enrolled in Cohort 1 (either 1a or 1b), there will be a second protocol liver biopsy performed 12 weeks after transplantation for central laboratory assessments.

For subjects enrolled in Cohorts 2, 3, or 4, there are two additional protocol biopsies after the initial, back table biopsy. The second protocol liver biopsy will be obtained approximately 10-14 weeks after transplantation, and approximately 7 – 10 days prior to darTreg infusion to ensure that darTregs will only be infused in the context of a normal allograft with essentially normal allograft histology and the absence of any diagnostic criteria for AR or CR. Eligibility criteria D will be assessed with local pathology information. However, slides and additional tissue will be collected for a central reading and mechanistic assays. The darTregs eligibility biopsy does not have to be repeated if a second preparation of darTregs is manufactured and infusion of the product is delayed. The third and last protocol liver biopsy for Cohorts 2, 3, or 4 will be one week after darTreg infusion for central laboratory assessments.

There will be up to two passes for each protocol biopsy. Up to one additional pass might be required during clinically indicated (standard of care) biopsies to obtain adequate tissue for the planned mechanistic studies. The same set of specimens will be collected for each 16g biopsy (protocol driven or clinically indicated/for cause) in the following priority: 1) 1.5 cm fixed in formalin for histopathology; 2) 1.5-2.0 cm in buffered saline for detection of deuterium labeled cells; 3) 0.5-1cm in RNALater for gene expression and other mechanistic studies.

Confidential Page 45 of 80

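### Section 4.3.5 bars darTreg infusion only for rejection on the protocol biopsy, so after a delayed infusion it does not reach non-severe rejection found on a later clinically indicated biopsy

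*Protocol*

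**What the plan says.** Criterion D10 appears twice in the protocol.

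- Synopsis, Exclusion criteria D: "Evidence of AR or CR according to Banff criteria on allograft biopsy on local assessment".
- Section 4.3.5: "Evidence of AR or CR according to Banff criteria on protocol allograft biopsy based on local assessment".

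Section 8.3 treats protocol and for-cause biopsies as two kinds: "The same set of specimens will be collected for each 16g biopsy (protocol driven or clinically indicated/for cause". It places the eligibility biopsy in time, "The second protocol liver biopsy will be obtained approximately 10-14 weeks after transplantation", about 7 to 10 days before infusion. Its purpose is that cells go only into a graft with "essentially normal allograft histology and the absence of any diagnostic criteria for AR or CR".

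For a repeat manufacture, 8.3 says: "The darTregs eligibility biopsy does not have to be repeated if a second preparation of darTregs is manufactured and infusion of the product is delayed". Section 5.1.3 agrees: "Except for liver biopsy, the laboratory components of Screen D must be repeated within 10 days of planned infusion to ensure eligibility". It sets the outer limit: "infusion of darTregs must take place no later than 20 weeks after transplantation". Appendix 3, footnote 1, repeats the biopsy exemption.

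Section 10.5 calls for a biopsy to confirm any clinical suspicion of rejection before it is treated, so newer histology can exist by the time of a delayed infusion.

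**The concern.** D10 is the only pre-infusion criterion that looks at graft histology. In 4.3.5 it points to one named biopsy. When infusion is delayed, that biopsy ages while the Screen D laboratory tests are renewed. If a for-cause biopsy in the interval shows mild or moderate AR, 4.3.5 does not count it.

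One investigator could follow 4.3.5 and infuse. Another could follow the synopsis wording, or the aim in 8.3, and withhold. Eligibility criteria should give one answer for one subject. What is at stake is the safety of an individual subject: section 9.3.2 itself names infused donor-reactive effector cells as a theoretical contributor to rejection, and section 9.2 warns that the reduced dosing may raise rejection risk.

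**Working it through.** The plan gives no figure for this point, so there is none to reproduce. The check has three parts.

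**1. Does another rule catch the case?** Take a subject on everolimus with a clean eligibility biopsy, a failed first product, and mild AR on a later for-cause biopsy. The AR is treated by raising tacrolimus within the permitted ceiling, and ALT settles.

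| Rule | Effect on this subject |
|---|---|
| 4.3.5 D10 | Not met: the AR is not on the protocol biopsy |
| D6, ALT above 1.5 x ULN within 10 days | Not met once ALT has settled |
| D7, tacrolimus trough above 8 µg/L | Not met if the trough is 8 or lower |
| D9, mycophenolate within 10 days | Not met if none was given; does not apply to tacrolimus-based subjects |
| 6.1.4, steroids stopped by day 44 | A treatment rule, not a criterion D |
| 7.1 items 3 to 5 | Cover severe AR, CR and steroid-refractory rejection; not mild or moderate AR that responds |
| 7.1 item 7, investigator decision on future study treatment | Can cover it, but is permissive |
| Appendix 1, footnote 11 | Ties the start of expansion to continuing eligibility, which leads back to the same criteria |

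Nothing in 4.3.5 bars infusion. Only judgment under 7.1 does.

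**2. How old can the histology be at infusion?**

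- As planned (8.3): 7 to 10 days.
- One quick repeat, assuming a 2 to 3 week expansion (Appendix 1, footnote 11) restarted on the planned infusion day: 7 + 14 = 21 to 10 + 21 = 31 days.
- Outer limit set by week 20: (20 − 14) x 7 = 42 to (20 − 10) x 7 = 70 days.

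Screen D laboratory tests may be at most 10 days old.

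**3. How many subjects might be affected?**

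Inputs:

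- Product failure: 2 of 16 in the same group's diabetes trial (section 1.4), used as a proxy for repeat manufacture. 2/16 = 12.5%, exact (Clopper-Pearson) 95% CI 1.6% to 38.3%.
- Infused subjects: 3 + 3 + 6 = 12. Expected repeats: 12 x 0.125 = 1.5 (0.2 to 4.6).
- One-year treated biopsy-proven AR: 2.9% and 7.0% in the two arms cited in section 1.2.3, spread evenly over the year.

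Formula: expected subjects = repeats x annual AR x gap in days / 365.

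| Assumption | AR risk in the gap | Expected subjects of 12 |
|---|---|---|
| 21 days, 2.9% | 0.029 x 21/365 = 0.17% | 1.5 x 0.00167 = 0.0025 |
| 31 days, 7.0% | 0.070 x 31/365 = 0.59% | 1.5 x 0.00595 = 0.009 |
| 70 days, 7.0% | 0.070 x 70/365 = 1.34% | 1.5 x 0.01342 = 0.020 |
| 70 days, 7.0%, upper limit of repeats | 1.34% | 4.6 x 0.01342 = 0.06 |

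An even spread may be wrong in either direction: section 1.2.5 expects less rejection in this period, and section 9.2 warns of more. With an assumed five-fold rate, the first and third rows become 5 x 0.0025 = 0.013 and 5 x 0.020 = 0.10. Stacking the five-fold rate, 70 days and 4.6 repeats gives 5 x 0.062 = 0.31. If cohorts 2 and 3 both expand to six, 18 subjects are infused and every figure rises by 18/12 = 1.5, so the stacked figure is about 0.46. These counts include severe AR and AR that D6 would stop, so on each set of assumptions they overstate the residual case.

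**The case against.** The best reply is that there is no true contradiction. The only pre-infusion biopsy scheduled for Screen D is the protocol eligibility biopsy. The synopsis may therefore be shorthand for it, with 4.3.5 merely giving the full name. The words in 8.3 are a purpose clause attached to that biopsy, not a free-standing rule on for-cause biopsies, and the same section deliberately waives a repeat. This stands, and it limits the point: the synopsis does not settle the case, and the conflict is with the aim of 8.3, not with an explicit rule. But waiving a routine repeat is not the same as disregarding a positive biopsy that was taken anyway.

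Second, an investigator would probably not infuse soon after diagnosing AR. Item 7 of 7.1 gives clear authority to withhold, elevated liver tests are reportable (14.4.1), and the PI and medical monitor review safety data continuously (14.8). This also stands as a reason why the case is rare. It leaves the decision to discretion where the protocol otherwise uses a criterion.

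A reader might infer more than the documents support:

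- *That the protocol sanctions infusion during rejection.* It does not. It leaves one sequence of events unaddressed by D10, with discretionary backstops.
- *That the risk is heightened because the product is untested in humans.* Section 1.4 says it has not been used before, but section 4.4 describes another trial with the same product and section 9.3.2 speaks of limited experience. The point does not need this argument.
- *That event rates or stopping rules are affected.* Nothing here supports that.

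**Conclusion.** The point holds as a minor defect. The safety criterion in 4.3.5 is drawn more narrowly than the synopsis wording and than the aim in 8.3. The difference matters only when a repeat manufacture delays infusion and a for-cause biopsy in the interval shows non-severe AR that the other criteria miss.

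The expected number affected is well under one in 12: roughly 0.0025 to 0.02 on the central proxy for repeats, 0.06 at the upper limit of repeats, and 0.31 with an assumed five-fold AR rate added. These figures rest on a failure rate from a polyclonal product in diabetic patients, where the two affected subjects were withdrawn and not remanufactured, and on AR rates from a trial of a comparable but different regimen. The gap in the wording itself rests on the text alone and does not depend on those rates.

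**What to change.** Put the same sentence in the synopsis and in 4.3.5 as criterion D10: *AR or CR by Banff criteria, on local assessment, on the protocol eligibility biopsy or on any later clinically indicated allograft biopsy before darTreg infusion.*

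The wording should be additive. A test based on the most recent biopsy may look neater, but it would loosen the present rule, because a clean for-cause biopsy could then override AR on the eligibility biopsy. Neither D10 wording provides for that now.

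The change adds no biopsy and keeps the waiver of a repeat. Local pathology from unscheduled visits is already collected (10.5). The cost is a protocol amendment to two lines and one rare consequence: a subject already given Thymoglobulin, including one whose later AR has resolved, would not be infused and would go to the replacement review in 13.3 (NIAID medical monitor, PI and two independent transplant physicians).
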